**Inference Criteria, Including Any Adjustments for Multiple Comparisons:**

We will not perform any corrections for multiple hypothesis testing, and we will use two-tailed tests with p-values  $\leq 0.05$  to denote statistically significant effects.

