#### **Total Number of Observations:**

N = 42,470 households eligible for Cost-Sharing Reduction (CSR) Silver 94 plans but enrolled in non-silver tier plans in late-June 2021.

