#### **Randomization / Assignment:**

Randomization was done at the household level. 75% of households were randomly assigned to two informational emails in late June and mid-July, respectively, and the remaining 25% were randomly assigned to no outreach during the intervention period beyond an eligibility redetermination notice.

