#### **Power:**

To arrive at an estimate for the minimum detectable effect (MDE) for our primary outcome, we assume a baseline metal tier switch rate of 10 percent. The intervention was powered at the 80% level to detect a 1 percentage point increase in the CSR Silver enrollment rate.

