#### **Likely Effect Size:**

Based on prior choice error nudges carried out by Covered California, we would expect to observe an ITT effect between 1-4 percentage points.

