### *Data and Data Structure*

#### **Outcomes:**

The primary outcome of interest will be an indicator for whether a consumer is enrolled in a CSR Silver plan by the end of July 2021. Our secondary outcomes will include (1) an indicator for whether someone had an office visit between July 2021 and December 2021 (2) an indicator for whether someone had a prescription drug fill between July 2021 and December 2021, (3) an indicator for whether someone had

an emergency room visit between July 2021 and December 2021, (4) an indicator for whether someone had a hospital admission between July 2021 and December 2021.

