**Follow-Up Analyses**

We will examine treatment heterogeneity by self-reported race and ethnicity, baseline metal tier, age bracket and income bracket. In addition, as part of our complier average causal effect analysis, we will examine the effects of CSR Silver enrollment (among households induced to enroll in a CSR Silver plan as a result of random assignment) on our four utilization outcomes.

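### Should the 0.05 significance rule be changed because the four utilization outcomes are likely to be poorly powered?

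*SAP*

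**What the plan says.** Under Inference Criteria, the SAP states "We will not perform any corrections for multiple hypothesis testing, and we will use two-tailed tests with p-values" at or below 0.05 marking a statistically significant effect. Primary and secondary outcomes are not treated differently.

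The Power section concerns the primary outcome: "we assume a baseline metal tier switch rate of 10 percent", and "The intervention was powered at the 80% level to detect a 1 percentage point increase in the CSR Silver enrollment rate". Under Likely Effect Size, "we would expect to observe an ITT effect between 1-4 percentage points". The sample is "N = 42,470 households eligible for Cost-Sharing Reduction (CSR) Silver 94 plans", and "75% of households were randomly assigned to two informational emails in late June and mid-July, respectively, and the remaining 25% were randomly assigned" as controls, who got only an eligibility notice.

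The Outcomes section makes CSR Silver enrollment the primary outcome. The sentence beginning "Our secondary outcomes will include" then lists four yes/no indicators for July to December 2021: office visit, prescription fill, emergency room visit and hospital admission. Statistical Models applies one unadjusted ITT regression to whichever outcome is studied. Under Follow-Up Analyses, "we will examine the effects of CSR Silver enrollment" on those four outcomes by instrumental variables. No base rate, expected effect or power is given for any utilization outcome.

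**The concern.** The emails urge a change of plan. They should alter care use mainly through the few households that switch because of them, which is also the premise of the instrumental-variable analysis. If 1 to 4 households in 100 are moved, any effect of CSR Silver on care use is diluted 25- to 100-fold in the ITT comparison. A design sized for a 1 point change in enrollment then has little chance of detecting it.

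Attaching the same label at the same threshold to these outcomes invites two misreadings. A non-significant result could be taken to show that richer coverage does not change care use. A significant result could be taken at face value although, with low power, estimates that cross the threshold tend to be too large. The question is whether the inference rule should therefore be confined to the primary outcome.

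**Working it through.** **Inputs from the SAP.** N = 42,470, split 75:25, so n1 = 31,852.5 and n0 = 10,617.5; two-sided 0.05; 10% baseline for the primary outcome; enrollment effect 1 to 4 points.

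**Assumed inputs.** Utilization base rates of 3% to 50%; effects of CSR Silver on utilization of 3 to 20 points; one observation per household; complete utilization data; no effect of the emails except through enrollment.

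**1. The plan's own figure.** For 10% against 11%, the pooled rate is 0.25 × 0.10 + 0.75 × 0.11 = 0.1075.
- SE under the null = √(0.1075 × 0.8925 × (1/n0 + 1/n1)) = 0.347 points.
- SE under the alternative = √(0.10 × 0.90/n0 + 0.11 × 0.89/n1) = 0.340 points.
- Power = Φ((1 − 1.96 × 0.347)/0.340) = 82.7%.

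The effect detectable with 80% power is 0.97 points. The stated 80% for 1 point is reproduced, slightly on the safe side.

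**2. Precision for utilization.** k = 1/n0 + 1/n1 = 1.2558 × 10⁻⁴ and SE = √(p(1−p)k). The significance threshold is 1.96 × SE. The difference detectable with 80% power is (1.96 + 0.842) × SE. All figures are in percentage points.

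| Assumed base rate | SE | Threshold | Detectable difference | CSR Silver effect implied at a 1 point / 4 point enrollment effect |
|---|---|---|---|---|
| 50% | 0.560 | 1.098 | 1.570 | 157 / 39 |
| 10% | 0.336 | 0.659 | 0.942 | 94 / 24 |
| 3% | 0.191 | 0.375 | 0.536 | 54 / 13 |

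The last column is the detectable difference divided by 0.01 and by 0.04.

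**3. Power per outcome.** With d = enrollment effect × CSR Silver effect, power = Φ(d/SE − 1.96) + Φ(−d/SE − 1.96). For example, at a 50% base rate, a 10 point CSR Silver effect and a 4 point enrollment effect, d = 0.4, d/SE = 0.714 and power = 0.106 + 0.004 = 11.0%.

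| Base rate | CSR Silver effect | Power at 1 point enrollment effect | Power at 4 points |
|---|---|---|---|
| 50% | 10 | 5.4% | 11.0% |
| 50% | 20 | 6.5% | 29.8% |
| 20% | 10 | 5.6% | 14.5% |
| 10% | 5 | 5.3% | 9.1% |
| 10% | 10 | 6.0% | 22% |
| 3% | 3 | 5.3% | 9.6% |
| 3% | 10 | 8.2% | about 54% |

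A 50% base rate has the largest variance. For a given CSR Silver effect it therefore gives the lowest power, and 11% is not a ceiling. The 3% row with a 10 point effect is extreme, because a 10 point rise would more than quadruple the rate and a 10 point fall is impossible.

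**4. What the SAP claims.** Set beside these figures, the Power section promises nothing for utilization, so no stated power is missed. The Outcomes section already ranks the four indicators below enrollment. The Inference Criteria say when a result is called significant; they do not say what p above 0.05 means.

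**The case for a change.** The strongest case for a change does not depend on a guessed CSR Silver effect. At a 50% base rate and the 1 point enrollment effect the trial is sized for, suppose every household induced to switch went from no visit to a visit. Then d/SE = 1/0.560 = 1.785 and power is only 43%. With a 10 point CSR Silver effect, the true ITT difference is 0.1 to 0.4 points, so an estimate must be at least 1.098/0.4 = 2.7 to 1.098/0.1 = 11 times too large to reach the threshold. In simulation, the chance of at least one significant result among the four is 13% to 19% with no effect (correlation 0.7 to 0). It is 14% to 20% at a 1 point enrollment effect and 23% to 35% at 4 points, with CSR Silver effects of 10, 10, 5 and 3 points. At 1 point the label hardly separates effect from no effect, and a remedy would cost only wording.

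The dilution and the risk of misreading stand as cautions for interpretation. The rest does not carry a change:

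- Low power neither invalidates a two-sided 0.05 test nor raises its per-test error. The any-of-four figure under no effect (1 − 0.95⁴ = 18.5% for independent tests) is a multiplicity matter, and the SAP is open about making no correction.
- The exaggeration depends on the scenario. At a 4 point enrollment effect the threshold is 0.659/0.4 = 1.65 times the true difference at a 10% base rate with a 10 point effect, and 1.098/0.8 = 1.37 times at 50% with 20 points.
- A 95% interval that excludes zero is the same test as p ≤ 0.05. Withholding the word significant while reporting intervals changes the label and not the inference, and statisticians reasonably differ on that convention.
- Confining such a rule to the ITT differences would leave the instrumental-variable estimates on the same outcomes under the 0.05 rule.

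**Conclusion.** No change to the plan follows. The utilization tests probably have little power: about 5% to 11%, 6% to 22% and 5% to 10% in the three scenarios given above, as the enrollment effect runs from 1 to 4 points. Larger CSR Silver effects give more, up to about 54% in the extreme 3% case. Every one of these figures rests on base rates and CSR Silver effects that the SAP does not give, and on the emails acting only through enrollment.

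This is an ordinary limit of secondary outcomes in a trial sized for its primary one, and the SAP does not pretend otherwise. Assignment has already been made, so wording cannot add power. The imprecision will also be visible in the results. Ignoring uncertainty in the enrollment effect, a 95% interval for the instrumental-variable estimate at a 50% base rate has a half-width of about 1.098/0.04 = 27 points at a 4 point enrollment effect and 1.098/0.01 = 110 points at 1 point. Detectable differences are missing detail that analysts can supply from observed control rates. A report that shows both sets of utilization estimates with their intervals, and does not read a non-significant result as no effect, meets the concern within the plan as it stands.
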